STUDY PROTOCOL

1. Title of the Study

Clinical Profile of Appendicitis and Comparative Study of Harmonic Scalpel (Seal and Cut) Versus Suture Ligation of the Base of Appendix During Laparoscopic Appendectomy

2. Protocol ID & Registration

Protocol ID: GSVM/GENSURG/APP/2025

ClinicalTrials.gov Identifier (NCT Number): [To be added]

Trial Registration Registry: ClinicalTrials.gov

3. Principal Investigator

Name: [name]

Designation: Principal Investigator

Affiliation: Department of General Surgery, GSVM Medical College, Kanpur, India

Email: [contact]

[contact]

4. Research Guide / Senior Author

Name: Dr. [name]

Designation: Professor & Head

Department: General Surgery, GSVM Medical College, Kanpur

5. Background and Rationale

Acute appendicitis is a common surgical emergency. Laparoscopic appendectomy is widely accepted, with secure closure of the appendix base being a critical step. The harmonic scalpel offers an energy-based alternative to traditional suturing. This study aims to compare outcomes between these two techniques.

6. Study Objectives

Primary Objective:

- To compare operative time between harmonic scalpel and suture ligation techniques.

Secondary Objectives:

- To evaluate postoperative complications (leak, ileus, SSI)
- To assess hospital stay duration
- To document appendix position intraoperatively

7. Study Design

Study Type: Interventional (Clinical Trial)

Allocation: Randomized (computer-based)

Interventional Model: Parallel Assignment

Masking: Single (Participant)
Number of Arms: 2
Primary Purpose: Treatment

8. Participants

Sample Size: 60 patients (30 per group)

Inclusion Criteria:

- Age 15–60 years
- Diagnosed with uncomplicated acute appendicitis
- Consent to participate

Exclusion Criteria:

- Perforated/gangrenous appendix
- Pregnancy
- Coagulopathy or severe comorbid illness

9. Interventions

Arm A: Harmonic Scalpel Group (Experimental)

Laparoscopic appendectomy using harmonic scalpel to seal and divide appendix base.

Arm B: Suture Ligation Group (Active Comparator)

Laparoscopic appendectomy with intracorporeal suture ligation of appendix base.

10. Outcome Measures

Primary Outcome:

- Operative time (in minutes)

Secondary Outcomes:

- Position of appendix (intraoperative)
- Postoperative leak (within 7 days)
- Postoperative ileus (within 3 days)
- Surgical site infection (within 30 days)
- Hospital stay (in days)

11. Ethical Considerations

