Approved by Institutional Ethics Committee, GSVM Medical College

Informed written consent will be obtained from all participants

Trial will be registered with ClinicalTrials.gov

12. Data Sharing Statement

De-identified individual data will be shared upon request for secondary analysis after 6 months of publication.

13. Timeline

Study Start: [April 2024]

Estimated Completion: [e.g., July 2025]

14. Funding and Support

No external funding. Supported by institutional resources.

Date- 01/05/2025

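### Does a protocol dated 2025 for a study started in April 2024 mean that the outcomes were fixed late and the plan must change?

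*Protocol*

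**What the plan says.** Section 13 (Timeline) has two entries, both in square brackets: "Study Start: [April 2024" and "Estimated Completion: [e.g., July 2025". After section 14 an unlabelled line reads "Date- 01/05/2025". Section 2 has "Protocol ID: GSVM/GENSURG/APP/2025" and "ClinicalTrials.gov Identifier (NCT Number): [To be added".

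Section 11 (Ethical Considerations) puts two statements in the future tense, "Trial will be registered with ClinicalTrials.gov" and "Informed written consent will be obtained from all participants", and one in the past tense, "Approved by Institutional Ethics Committee, GSVM Medical College". The approval carries no date.

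The protocol has no version number, version history or recruitment status, and it does not say when the outcomes were first set. Operative time is primary in both section 6 and section 10. Section 10 sets windows of 3, 7 and 30 days for ileus, leak and surgical site infection. Section 7 masks participants only.

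**The concern.** A protocol is expected to precede the trial it governs. Here the closing date, the year in the protocol ID and the empty registry number all point to 2025, while the start is given as April 2024. Taken at face value, the document was written, and registration was still outstanding, well into the recruitment period.

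The operating team knows each patient's arm, and operative time is known as each case ends. Someone choosing the primary outcome or the complication windows in 2025 could therefore have done so knowing how the arms compared. If that had happened, the trial could not claim a pre-specified primary outcome, and a report that called the registration prospective would be wrong.

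**Working it through.** **Inputs.** Start: April 2024, taken as any day from 1 to 30 April (section 13). Completion: July 2025, taken as any day from 1 to 31 July (section 13, bracketed and marked as an example). Document date: 1 May 2025 if day comes first, 5 January 2025 if month comes first (closing line). Sample size: 60 (section 8). The protocol gives no elapsed-time figure to reproduce.

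**Days from start to document date.**

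| Document date | From 1 April 2024 | From 30 April 2024 |
|---|---|---|
| 1 May 2025 | 395 | 366 |
| 5 January 2025 | 279 | 250 |

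This is about 12 to 13 months on the first reading and 8 to 9 months on the second. The document follows the stated start on both.

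**Share of the stated span.** Share = days from start to document date ÷ days from start to completion. The span is 456 to 486 days from 1 April 2024, and 427 to 457 days from 30 April 2024.

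- 1 May 2025: lowest 366/457 = 0.801, highest 395/456 = 0.866.
- 5 January 2025: lowest 250/457 = 0.547, highest 279/456 = 0.612.

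**Patients, if accrual were even (an assumption).** 60 × 0.801 to 60 × 0.866 gives 48 to 52. 60 × 0.547 to 60 × 0.612 gives 33 to 37. The overall range is 33 to 52 of 60. It depends on a placeholder end date, an ambiguous document date and an accrual pattern that the protocol does not state, so it illustrates scale and is not evidence of enrolment.

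**Do the statements contradict each other?** Suppose a trial began in April 2024 with ethics approval, was written up in this form in 2025, and was to be registered afterwards.

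- The start date and the document date are both true.
- The empty registry number and the promise of registration are both true.
- The approval, in the past tense, is true.
- The consent sentence is ordinary protocol wording, and it holds for any patient still to be enrolled.

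Every line is satisfied, so the passages describe late registration and do not contradict one another.

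**Do they date the outcomes?** No line says when the outcomes were chosen. The closing date could be a version, signature or upload date. The ethics approval shows that something had been approved before this text was finished, but without a date it cannot show which outcomes were approved, or when.

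**The case for a change.** The strongest case for acting is that the protocol itself states the start date, its own date and the registration status, so none of this can be left to a statistical analysis plan. Either April 2024 is right and registration cannot have preceded enrolment, or the timeline is wrong; both deserve correction. The elapsed share is not inflated either. If completion includes the 30-day follow-up for surgical site infection, accrual ends 30 days sooner and the shares rise to 366/427 = 0.86 up to 395/426 = 0.93 for 1 May, and to 250/427 = 0.59 up to 279/426 = 0.65 for 5 January. With surgeons unmasked, evidence that outcomes were set early is what a reader would want, and the correction costs only wording.

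The dates and arithmetic stand, and so does the limited conclusion that registration before first enrolment is unsupported and the timing of the outcomes cannot be verified from this document. What does not stand is the step from unverified to late. The protocol nowhere describes itself as prospectively registered and openly shows registration as pending. Operative time is primary wherever the primary outcome is named, with no trace of a switch. The brackets and the example marker suggest unfinished template fields, so the timeline may itself be unconfirmed.

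**Conclusion.** No change to the plan follows. On its own dates the document comes 250 to 395 days after the stated start with registration outstanding, so it cannot support a claim of registration before enrolment. It makes no such claim, and it does not show that any outcome was chosen after data were seen.

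The remedy would be to record dates, registration status and a disclosure about outcome changes. That is useful housekeeping, and any report should describe the registration timing accurately. But randomisation, arms, outcomes, windows and sample size would stay as they are, and no rule in the protocol gives a wrong result if followed as written. This is missing detail about the document's history, with no gain to the design or analysis from filling it in.

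The conclusion assumes that the bracketed April 2024 start is at least roughly right. If it is only a leftover template entry, the apparent late start becomes a clerical slip. It does not rely on the patient counts.
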